### 8.3 BOLD/TOLD MRI

The BOLD/TOLD MRI sequences will be added to the routine MRI sequences (T1, T2 etc.) performed at baseline and at follow-up, which may require additional time on the MRI table (~30minues), but will not require any additional infusions or intravenous contrast as described in literature previously [98, 99]. These additional sequences will be optional.

### 8.4 Tumor respiratory motion modeling

Real-time optical surface monitoring data will be acquired from human patients with primary or metastatic kidney lesions during and after their 4DCT scan (standard-of-care at our institution). A patient-specific 4D model will be developed using the raw 4DCT projections time-correlated with real-time surface monitoring. In addition, before delivering each dose fraction, we will acquire three 15s kV fluoroscopic image acquisitions, time-correlated with optical surface monitoring. The acquisitions will be distributed over three well-spaced beam angles, e.g., every 4th angle for a 12-field plan.

The kV fluoro data will be used offline to update and validate the model as follows. The data acquired from the three beam angles will be used in a "missing-view" fashion, i.e., two of the three fluoro sequences will be used to update the model and the third will be used to validate the model. The ground truth will be the in-plane X-Y trajectories of features-of-interest obtained from kV fluoro. The model will be used to create 2D+t digitally reconstructed fluoroscopic series (DRFs) from the beam's eye view of each kV beam. The model will be validated by calculating the geometric error between the trajectories from the kV fluoro (ground truth) and those obtained from the corresponding DRFs.

**Surface monitoring procedure** —The procedure is expected to last approximately 15 minutes after the end of the 4DCT scan, which is the standard-of-care at our institution. The procedure will consist of real-time surface tracking using the VisionRT system of the thoracic and/or abdominal region. Continuous audiovisual contact will be maintained with the subject during scanning. Each individual will be informed that they can stop the procedure at any point.

**Fluoroscopic imaging procedure** — Fluoroscopic imaging will be performed in the treatment room with the patient lying in treatment position. Three 15s acquisitions will be performed under free breathing conditions, each from a different beam angle, using the on-board kV imager. Audiovisual contact will be maintained at all times with the patient.

All surface monitoring will be performed using a surface photogrammetry system (VisionRT, London, UK) which uses visible light to monitor the motion of the surface. There are no known significant risks with this procedure at this time. This device and procedure is low-risk.

For the fluoroscopic acquisition, we estimate that for three 15 s acquisitions, each at 10 frames/s, 120 kVp, 40 mA, 10 ms, with 0.1 mGy/mAs, the total skin dose will be ~24 mGy — comparable to that from a kV cone-beam CT (CBCT) scan [100, 101]. Daily CBCT is standard-of-care for patient localization for SBRT at UT Southwestern. No additional ionizing radiation, other than the kV fluoro and standard-of-care, will be administered to the patient as a result of this aspect of the study.

## 8.5 Specimen Banking

Subject samples collected for this study will be retained at the department of pathology and at the lab of [name] (NC7. 208). Specimens will be stored indefinitely or until they are used up. If future use is denied or withdrawn by the subject, best efforts will be made to stop any additional studies and to destroy the specimens.

[name] will be responsible for reviewing and approving requests for clinical specimen from potential research collaborators outside of UTSW. Collaborators will be required to complete an agreement (a Material Transfer Agreement or recharge agreement) that states specimens will only be released for use in disclosed research. Any data obtained from the use of clinical specimen will be the property of UTSW for publication and any licensing agreement will be strictly adhered to.

The specimens, DNA, and their derivatives may have significant therapeutic or commercial value. The Informed Consent form contains this information and informs the subject that there is the potential for financial gain by UTSW, the investigator or a collaborating researcher or entity.

The following information obtained from the subject's medical record may be provided, among other, to research collaborators when specimens are made available:

- Diagnosis
- Collection time in relation to study treatment
- Clinical outcome – if available
- Demographic data

## 9.0 STATISTICAL CONSIDERATIONS

### 9.1 Study Design/Study Endpoints

This is an open label single-arm phase II non-randomized prospective single arm study that treats a single SRM with SABR. The primary objective is local control of the SRMs. Local control is defined as less than 4mm increase in the longest diameter of tumor measured using either MRI or contrast enhanced CT scan and with no radiographic or pathologic evidence of viable tumor. The endpoint will be measured at a minimum follow up of one year. Secondary objections and endpoints explore the safety, toxicity, growth, growth rate, local failure, IDR, immune response and progression of the SRMs after SABR.

The stopping rules for this study include any treatment-related >grade 3 toxicity. If there are any treatment related grade 3 acute toxicity in >30% of enrolled patients after enrollment of at least 6 patients, the study will be suspended until permitted by a safety review.

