### 7.3.1 **Reporting SAEs and UPIRSOs to the Simmons Comprehensive Cancer Center (SCCC) Data Safety Monitoring Committee (DSMC)**

All SAE/UPIRSOs at all sites, which occur in research subjects on protocols for which the SCCC is the DSMC of record require reporting to the DSMC regardless of whether IRB reporting is required. All SAEs/UPIRSOs occurring during the protocol-specified monitoring period should be submitted to the SCCC DSMC within 5 business days of the PI or delegated study team members awareness of the event(s). In addition, for participating centers other than UTSW, local IRB guidance should be followed for local reporting of serious adverse events.

The UTSW study team is responsible for submitting SAEs/UPIRSOs to the SCCC DSMC Coordinator. Hardcopies or electronic versions of the eIRB Reportable Event report; FDA Form #3500A forms, or other sponsor forms, if applicable; and/or any other supporting documentation available should be submitted to the DSMC Coordinator. The DSMC Coordinator forwards the information onto the DSMC Chairman who determines if immediate action is required. Follow-up eIRB reports, and all subsequent SAE/UPIRSO documentation that is available are also submitted to the DSMC Chair who determines if further action is required. *(See Appendix III of the SCCC DSMC Plan for a template Serious Adverse Event Form which may be utilized when a sponsor form is unavailable and SAE submission to the eIRB is not required).*

If the event occurs on a multi-institutional clinical trial coordinated by the UTSW Simmons Comprehensive Cancer Center, the DOT Manager or lead coordinator ensures that all participating sites are notified of the event and resulting action, according to FDA guidance for expedited reporting. DSMC Chairperson reviews all SAEs/UPIRSOs upon receipt from the DSMC Coordinator. The DSMC Chairperson determines whether action is required and either takes action immediately, convenes a special DSMC session (physical or electronic), or defers the action until a regularly scheduled DSMC meeting.

The following instructions section may be modified as needed to ensure clear guidance for institutions participating in the trial who will not report directly to the UTSW Institutional Review Board. If needed, this reporting may be facilitated by the UTSW study team for example.

Telephone reports to: (Investigator/study team: Insert names and phone numbers for required notifications)

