### **Reporting Unanticipated Problems Involving Risks to Subjects or Others (UPIRSOs) to the UTSW HRPP/IRB**

UTSW reportable event guidance applies to all research conducted by or on behalf of UT Southwestern, its affiliates, and investigators, sites, or institutions relying on the UT Southwestern IRB. Additional reporting requirements apply for research relying on a non-UT Southwestern IRB.

According to UTSW HRPP/IRB policy, UPIRSOs are incidents, experiences, outcomes, etc. that meet **ALL three (3)** of the following criteria:

1. Unexpected in nature, frequency, or severity (i.e., generally not expected in a subject's underlying condition or not expected as a risk of the study; therefore, not included in the investigator's brochure, protocol, or informed consent document), AND
2. Probably or definitely related to participation in the research, AND
3. Suggests that the research places subjects or others at a greater risk of harm (including physical, psychological, economic, or social harm) than was previously known or recognized. Note: According to OHRP, if the adverse event is serious, it would always suggest a greater risk of harm.

For purposes of this policy, UPIRSOs include unanticipated adverse device effects (UADEs) and death or serious injury related to a humanitarian use device (HUD).

UPIRSOs must be promptly reported to the UTSW IRB within 5 working days of PI awareness.

For research relying on a non-UT Southwestern IRB (external, central, or single IRB):

Investigators relying on an external IRB who are conducting research on behalf of UT Southwestern or its affiliates are responsible for submitting **LOCAL** UPIRSOs to the UT Southwestern IRB within 5 working days of PI awareness. Investigators must report to their relying IRB according to the relying IRB's policy. In addition, the external IRB's responses or determinations on these local events must be submitted to the UT Southwestern IRB within 10 working days of receipt.

Events NOT meeting UPIRSO criteria:

Events that do NOT meet UPIRSO criteria should be tracked, evaluated, summarized, and submitted to the UTSW HRPP/IRB at continuing review.

For more information on UTSW HRPP/IRB reportable event policy, see <https://www.utsouthwestern.edu/research/research-administration/irb/assets/policies-combined.pdf>.

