#### **7.4 Stopping Rules**

Interim analysis will be performed after enrollment of 6 patients. The stopping rules for study includes grade 3 acute toxicity in >30% of enrolled patients, and tumor progression/growth in >50% of enrolled patients.

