#### **10.5 Data Management and Monitoring/Auditing**

The monitoring activities are designed to provide safety monitoring, data quality assurance, and oversight of protocols for study progress. The Radiation Oncology Clinical Research Office (CRO) reports serious adverse events (SAEs) to Radiation Oncology Safety Assurance Committee (ROSAC) monthly. These SAEs are also reported to the University of Texas Southwestern Medical Center (UTSW) IRB and

Simmons Comprehensive Cancer Center DSMC. SCCC-DSMC will audit in accordance with the DSMC plan guidelines.

The purpose of the Radiation Oncology Safety Assurance Committee (ROSAC) is to ensure that clinical trial data is accurate and valid and to ensure the safety of trial participants. The plan complies with the Simmons Comprehensive Cancer Center (SCCC) Data Safety Monitoring Plan and the University of Texas Southwestern Medical Center (UTSW) IRB guidelines.

REDCap is the UTSW SCCC institutional choice for the electronic data capture of case report forms for SCCC Investigator Initiated Trials. REDCap will be used for electronic case report forms in accordance with Simmons Comprehensive Cancer Center requirements, as appropriate for the project

ROSAC is charged with developing, implementing, and maintaining the Data and Safety Monitoring Plan. The membership consists of a Medical Director of Clinical Research as well as representation from the following groups: clinical research, nursing, regulatory, pharmacy, physicists, radiation therapists, and faculty. Additional members are contacted to participate as needed.

Trial monitoring will be conducted no less than annually and refers to a regular interval review of trial related activity and documentation performed by the DOT and/or the CRO Multi-Center IIT Monitor. This review includes but is not limited to accuracy of case report forms, protocol compliance, timeliness and accuracy of Velos entries and AE/SAE management and reporting. Documentation of trial monitoring will be maintained along with other protocol related documents and will be reviewed during internal audit.

For further information, refer to the UTSW SCCC IIT Management Manual.

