The UTSW Simmons Comprehensive Cancer Center (SCCC) Data Safety Monitoring Committee (DSMC) is responsible for monitoring data quality and patient safety for all UTSW SCCC clinical trials. As part of that responsibility, the DSMC reviews all local serious adverse events and UPIRSOs in real time as they are reported and reviews adverse events on a quarterly basis. The quality assurance activity for the Clinical Research Office provides for periodic auditing of clinical research documents to ensure data integrity and regulatory compliance. A copy of the DSMC plan is available upon request.

The SCCC DSMC meets quarterly and conducts annual comprehensive reviews of ongoing clinical trials, for which it serves as the DSMC of record. The QAC works as part of the DSMC to conduct regular audits based on the level of risk. Audit findings are reviewed at the next available DSMC meeting. In this way, frequency of DSMC monitoring is dependent upon the level of risk. Risk level is determined by the DSMC Chairman and a number of factors such as the phase of the study; the type of investigational agent, device or intervention being studied; and monitoring required to ensure the safety of study subjects based on the associated risks of the study. Protocol-specific DSMC plans must be consistent with these principles.

Clinical trials are assessed for safety on a continual basis throughout the life of the trial. All SAE's and any AEs that are unexpected and definitely or probably related to study participation are reported to UTSW IRB through an electronic research system per UTSW IRB guidelines. SAEs are reported to the sponsor per specific sponsor requirements. These SAEs are reported to the SCCC DSMC on a real time basis. All local SAEs will be

reported to the SCCC DSMC. SAE reports can be either scanned/emailed to the coordinator of SCCC DSMC or sent through interoffice mail.

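### The grade 3 toxicity rule in section 9.1 waits for the sixth enrolment even after two affected patients have made suspension certain; a count rule would act sooner at little cost

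*Protocol*

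**What the plan says.** Section 9.1 of the protocol has two toxicity rules. The first has no minimum enrolment: "The stopping rules for this study include any treatment-related >grade 3 toxicity". The second covers treatment-related grade 3 acute toxicity and has a minimum: "grade 3 acute toxicity in >30% of enrolled patients after enrollment of at least 6 patients, the study will be suspended", with resumption depending on a safety review.

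Section 7.4 opens with "Interim analysis will be performed after enrollment of 6 patients" and continues directly with "The stopping rules for study includes grade 3 acute toxicity in >30% of enrolled patients", followed by a limit of more than 50% for progression or growth. Its rule sentence gives no minimum of its own, does not require the toxicity to be treatment-related, and omits the trigger above grade 3.

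Other oversight applies at any enrolment:

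- **Section 7.3.1:** on SAEs and UPIRSOs, "The DSMC Chairperson determines whether action is required and either takes action immediately" or takes one of two slower courses.
- **Section on reporting to the IRB:** "UPIRSOs must be promptly reported to the UTSW IRB within 5 working days of PI awareness".
- **Section 10.5:** the research office "reports serious adverse events (SAEs) to Radiation Oncology Safety Assurance Committee (ROSAC) monthly". The DSMC sees local SAEs and UPIRSOs as they are reported and "reviews adverse events on a quarterly basis".
- **Appendix B:** the principal investigator must verify every toxicity of grade 3 or higher; no time limit is given.

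**The concern.** A minimum denominator stops a percentage rule from firing on one event in a very small group. That purpose is already met when two patients are affected, because two is the number that crosses the limit at six. From then on, waiting for the sixth enrolment cannot change whether the review is held. It can only let more patients start treatment before it.

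The gap concerns grade 3 events. Related toxicity above grade 3 is a stopping rule at any enrolment. The fast reporting routes depend on an event being serious or an unanticipated problem, and what follows is left to judgement. For a grade 3 event that is neither, the protocol states no timed review faster than the quarterly one.

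At stake are up to four early patients in a 16-patient study, treated while a mandatory review is already inevitable.

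**Working it through.** **Inputs.** Limit above 30% and minimum of six enrolled: section 9.1. Planned size 16: section 9.2. The protocol gives no true rate of treatment-related grade 3 acute toxicity, so 5%, 10% and 20% are assumed.

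**The limit as a count.** The smallest number of affected patients k with k/n > 0.30 is:

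| Enrolled n | k that crosses |
|---|---|
| 6 | 2 (33.3%) |
| 7–9 | 3 |
| 10–13 | 4 |
| 14–16 | 5 |

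**Certainty before six.** If two are affected among the first m, at least 2/6 are affected at the sixth enrolment, which crosses. For m = 2, 3, 4, 5, the number who may still be enrolled first is 6 − m = 4, 3, 2, 1. This assumes the check is made when exactly six are enrolled. If it slips to seven, 2/7 = 28.6% no longer crosses, which also favours a count.

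**Expected saving.** Let d be the number of further enrolments before an event is known. If the second affected patient is number k, a count rule avoids 6 − k − d enrolments ahead of the review (zero if negative). The mean is the sum, over m from 2 to 5 − d, of P(at least 2 of m affected), where P(at least 2 of m) = 1 − (1−p)^m − m·p·(1−p)^(m−1).

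| True rate p | m=2 | m=3 | m=4 | m=5 | Mean, d=0 | Mean, d=1 |
|---|---|---|---|---|---|---|
| 5% | 0.0025 | 0.0073 | 0.0140 | 0.0226 | 0.05 | 0.02 |
| 10% | 0.0100 | 0.0280 | 0.0523 | 0.0815 | 0.17 | 0.09 |
| 20% | 0.0400 | 0.1040 | 0.1808 | 0.2627 | 0.59 | 0.32 |

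The m=5 column is also the chance that the situation arises at all with immediate reporting: 2.3%, 8.1% and 26.3%.

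**Which rates are plausible.** Section 1.3 reports only grade 1 acute events in the 15-patient phase I series; its one grade 3 event was late. Taking this as 0 of 15, the one-sided 95% upper limit is 1 − 0.05^(1/15) = 18.1%. At that rate the mean saving is 0.50 (d=0) or 0.27 (d=1). Doses varied in that series, so this is only a guide, but it puts 20% at the high end.

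**Does the change alter whether the study is ever suspended?** No, provided enrolment reaches six. Two known at or before six enrolled means 9.1 crosses at six, and from seven the limits are the same. Enumerating all 2^16 = 65,536 event sequences for 16 patients, with d = 0, 1 and 2, gives no sequence in which one rule suspends and the other never does.

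**Cost in reviews.** If the first review clears the study and a third affected patient is known by six enrolled, a review is added. With immediate reporting, P(at least 3 of 6) = 0.2%, 1.6% and 9.9% at 5%, 10% and 20%.

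**The case against.** The strongest reply is that 9.1 is clear and not wrong: a minimum before a percentage rule applies is sensible, and stopping once the boundary is certain to be crossed is a refinement. The saving is also small. Immediate knowledge is the favourable case, since the scheduled toxicity evaluation comes about four weeks after treatment (sections 5.2.3 and 5.4) and the acute window runs to the 12-week follow-up (section 7.2.1). Early patients also have real protection: the rule above grade 3, DSMC action on serious events, and investigator verification of every grade 3 event. Many grade 3 events would qualify as serious. All of this stands and sets the severity. It does not remove the gap, because none of these routes makes a review mandatory on two grade 3 cases before the sixth enrolment.

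A reader might go further and infer that 7.4 contradicts 9.1, because its rule sentence has no minimum and, taken alone, would be crossed by one affected patient among the first three (1/3 = 33.3%). The protocol does not support that. The limits in 7.4 directly follow the sentence setting the six-patient interim analysis and are most naturally what that analysis applies, so both sections act at six. Section 7.4 is only the looser of the two.

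**Conclusion.** The point holds as a low-severity improvement to a safety rule. Under 9.1, two known patients with treatment-related grade 3 acute toxicity among the first two to five make suspension at six certain, while one to four more may be enrolled first. At assumed rates of 5–10% the expected saving is about 0.02 to 0.17 patients, depending on how quickly events become known; at 20% it is 0.32 to 0.59. These are enrolments avoided ahead of the review; if the review clears the study, those places are filled later. The figures assume independent events, a common rate, and a check made when six are enrolled. The size of the gain does not make this a serious flaw, and the two sections should not be described as contradictory.

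**What to change.** Put the same text in 7.4 and 9.1:

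1. Suspend for safety review as soon as two patients with treatment-related grade 3 acute toxicity are known while six or fewer are enrolled. One such patient never suspends the study under this rule.
2. From the seventh enrolment, the existing limit of more than 30% applies.
3. After any review that permits continuation, at whatever enrolment, suspend again only when a new affected patient leaves the share above 30%.

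Sentence 3 must not be confined to the first six. If three of six are affected and the study is cleared, a seventh unaffected patient gives 3/7 = 42.9%, which would suspend it again with no new event.

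Keep the six-patient interim analysis and the rule above grade 3, and state the latter in 7.4 too. The cost is three sentences, with the same data and the same reviewers. The downsides are that the review may rest on fewer patients, and the small chance of an added review given above.

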## 9.2 Sample Size and Accrual

There is no reliable historic information on local control rate of SABR for primary RCC since the retrospective studies have used a wide range of SABR dose fractions and varying definitions of local failure. From the retrospective studies and one phase I trial, we found three local failures out of 34 patients (section 1.3). Thus, it is expected that the local control rate will be at least 90% in this trial. With a sample size of 16 patients, the standard error of local control rate will be at most 7.5% with a 95% confidence interval of 15%, since the local control rate is expected to be at least 90%.

A sample size of 16 patients in this single-arm phase II trial will have more than 90% power to detect the difference between 100% pre-treatment tumor growth and 50% post-treatment tumor growth using a two-sided binomial test with a 0.05 significance level. With the sample size of 16 patients in this single-arm phase II trial, a single group t-test with a two-sided 0.10 significance level will have 80% power to detect the difference between a pre-treatment tumor growth rate of 0.4 cm/year and a post-treatment tumor growth rate of 0.16 cm/year (a 60% reduction), assuming that the standard deviation is 0.36 cm/year. The power calculations were conducted using the software PASS 12.

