## 9.3 Data Analyses Plans

The local control rate and the proportion of patients whose tumors did not grow will be estimated along with the corresponding 95% confidence interval using the exact binomial method. The frequency of the adverse events associated with the administration of SABR to SRMs will be computed. Descriptive statistics such as mean, range, and 95% confidence interval will be computed for the growth rate of SRMs after SABR treatment, and the changes in kidney function, creatinine levels, renal perfusion and GFR after SABR treatment. Descriptive statistics will be also computed for radiographic changes of the SRM after SABR treatment, including tumor viability, %enhancement, necrosis, T2 signal, and tumor cellularity with diffusion-weighted imaging.

Kaplan-Meier method will be used to estimate the time to progression (TTP) of disease from the first SABR treatment, progression free survival (PFS), and overall survival (OS). Exploratory data analysis will be conducted to assess the cytokine changes brought on by SABR to SRM and to evaluate generation of any immune response specific to tumor cells.

We will compute the following characteristics of CT and MRI acquired prior to the treatment and follow-up scan: intensity features such as minimum, maximum, mean, standard deviation, median, skewness, kurtosis; texture features such as energy, entropy, correlation, inertia, cluster shade; geometry features such as volume, major axis length, minor axis length, eccentricity, elongation, roundness. The ability of each feature to predict treatment response will be quantified by the area under the receiver operating characteristic curve (AUC). An AUC of <0.7 will be considered to have low accuracy, 0.7-0.9 to have moderate accuracy, and >0.9 to have high accuracy.

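### The 15% precision quoted for n = 16 is a symmetric Wald margin that the planned exact interval does not deliver on its lower side, and the supporting count of 3 failures in 34 patients does not add up from section 1.3

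*Protocol*

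**What the plan says.** Section 9.2 of the protocol begins by conceding that the history on local control after SABR for primary RCC is unreliable. It then draws on earlier work: "From the retrospective studies and one phase I trial, we found three local failures out of 34 patients (section 1.3"). From this it concludes that "it is expected that the local control rate will be at least 90% in this trial", and states the precision: "standard error of local control rate will be at most 7.5% with a 95% confidence interval of 15" (percent). It does not say whether the 15% is a half-width or a full width.

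Section 9.3 fixes the method of analysis. The local control rate "will be estimated along with the corresponding 95% confidence interval using the exact binomial method".

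Section 1.3 describes five series of primary renal tumours with numbers: 9 patients (survival given, no local failure count), 33 lesions (94% local control), 8 patients (one local failure), 10 patients in a prospective phase II trial (no local failure count), and 15 patients in a phase I trial (two failures). It also mentions a retrospective series of 50 patients with primary and metastatic disease together, without a failure count.

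**The concern.** The precision statement and the analysis plan describe two different intervals. With 16 patients and a rate near 90%, a symmetric normal-theory margin is a poor guide to an exact interval. The exact interval is cut off at 100% above and extends well below the estimate. A reader of section 9.2 would expect a lower limit near 75% if the trial goes as planned. In a single-arm local control study the lower limit is what shows how poor the true rate could still be, so this is the part of the interval where optimism does most harm.

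The historical count matters because it is the only stated source of the 90% on which the precision depends. If it cannot be traced to the section it cites, the reader cannot check the planning rate.

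**Working it through.** **Inputs.** n = 16, planning rate 90%, confidence level 95% (section 9.2); exact binomial method (section 9.3); series sizes and failures (section 1.3).

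**The plan's own figure.**
- SE = √(0.9 × 0.1 / 16) = 0.075. This agrees with section 9.2.
- 1.96 × 0.075 = 0.147; 2 × 0.075 = 0.150. The 15% therefore reproduces as a Wald half-width.
- The implied interval is 0.900 ± 0.147, or 75.3% to 104.7%. The upper limit is impossible.
- Read instead as a full width, 15 points is narrower than any exact interval from 12/16 to 16/16; the smallest is 20.6 points, at 16/16.

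**The interval that section 9.3 prescribes.** For x controlled out of n, the exact (Clopper-Pearson) lower limit is the 2.5% quantile of Beta(x, n − x + 1), and the upper limit is the 97.5% quantile of Beta(x + 1, n − x). For 16/16 the lower limit reduces to 0.025^(1/16) = 0.794.

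| Controlled | Estimate | Exact 95% limits | Estimate minus lower limit | Half of full width | Probability at true 90% |
|---|---|---|---|---|---|
| 14/16 | 87.5% | 61.7–98.4% | 25.8 points | 18.4 points | 0.27 |
| 15/16 | 93.8% | 69.8–99.8% | 24.0 points | 15.0 points | 0.33 |
| 16/16 | 100% | 79.4–100% | 20.6 points | 10.3 points | 0.19 |

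Averaged over Binomial(16, 0.9):
- expected full width 32.9 points (half-width 16.4);
- mean distance from estimate to lower limit 24.5 points, so the expected lower limit is 90 − 24.5 = 65.5%.

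Only 16/16 has a lower limit above 75%, so at a true 90% the limit falls below 75% with probability 1 − 0.9^16 = 1 − 0.185 = 0.81.

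**The historical count.** The explicitly stated failures are 1 in the 8-patient series and 2 in the 15-patient phase I trial. The 33-lesion series at 94% control is read as 31/33, about 2 further failures (an assumption). The 50-patient mixed series is larger than 34 and gives no separate count for primaries.

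| Combination of primary-tumour series | Total | Failures stated or implied |
|---|---|---|
| 9 + 10 + 15 (the only one totalling 34) | 34 | 2 |
| 9 + 33 + 8 + 15 (retrospective plus phase I) | 65 | about 5 |
| 9 + 8 + 15 (same, without the 33 lesions) | 32 | 3 |
| 8 + 10 + 15 | 33 | 3 |

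The one combination that totals 34 omits the 8-patient series, which supplied the third failure. It also includes the phase II trial, although section 9.2 describes its sources as retrospective studies and one phase I trial.

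The effect on the planning rate is small. Control is 91.2% for 3/34, 90.6% for 3/32 and 92.3% for 5/65. Using the three series with a failure count or a control rate (33 + 8 + 15), 5/56 gives 91.1%. Series without a failure count are taken as contributing none.

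**The case against.** The protocol prints no interval running above 100%; it gives a standard error and an approximate margin. On half-width the exact figure is not far off: 15.0 points at 15/16 and 16.4 expected at a true 90%. At a true 95%, which is within the stated expectation, the expected half-width is 13.7 points. This stands, so the fault should not be described as a general failure of precision. It lies in the asymmetry: even at a true 95% the mean distance to the lower limit is 22.9 points.

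The consequence is also limited. Section 9.3 already prescribes the exact method, no decision rule depends on the 15%, and section 9.2 gives two power calculations for the same n. This stands too.

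A reader might go further in four ways that the documents do not support.

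- **That the standard error bound is wrong.** It is larger if the true rate is lower (10.0% at 80%), but section 9.2 makes the bound conditional on a rate of at least 90%, and under that condition it is correct.
- **That the t-test assumption contradicts 90% control.** Section 9.2 uses "a post-treatment tumor growth rate of 0.16 cm/year (a 60% reduction), assuming that the standard deviation is 0.36 cm/year". This is the alternative at which the test has its stated power, not a forecast of growth. Turning it into a share of tumours growing by 4 mm would also need a normal distribution and exactly one year of follow-up.
- **That section 1.3 supports clearly less than 90%.** Pooling only the two series with an explicit failure count (8 + 15) gives a lower rate, but that leaves out the 33-lesion series, which does report local control.
- **That the earlier series ignored tumour viability.** Section 1.3 does not say how they defined failure. Section 9.2 already acknowledges that the definitions varied.

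**Conclusion.** Two statements in section 9.2 need correction. First, the 15% interval is a Wald half-width and does not match the exact interval of section 9.3. The distance from estimate to lower limit is 21 to 26 points for 14 to 16 controlled patients, against the 15 stated. This rests on n = 16, the 90% planning rate and the Clopper-Pearson form of the exact interval. Second, the count of 3 in 34 cannot be derived from section 1.3 as written. Because most reconstructions give about 90–92% control, this is a traceability error and leaves the planning rate essentially unchanged; the 65- and 56-patient versions depend on reading 94% of 33 lesions as 31/33.

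Neither point affects the validity of the planned analysis or shows that 16 patients are too few. What is overstated is the planning-stage promise about the lower limit for the primary endpoint.

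**What to change.** In section 9.2:

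1. Remove the 15% confidence interval and state instead that, with 14, 15 or 16 of 16 patients controlled, the exact 95% limits are 61.7–98.4%, 69.8–99.8% and 79.4–100%. The expected lower limit of 65.5% at a true 90% can be added.
2. Keep the 7.5% standard error, worded as conditional on a true local control rate of at least 90%.
3. List the historical failures and patients series by series, say which of the series in section 1.3 are counted and why the others are not, and correct the total so that it adds up.

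This costs one paragraph of wording. Sample size, endpoint and method of analysis do not change. The only downside is that the stated precision looks less favourable.
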